## 4 STUDY DESIGN

### 4.1 OVERALL DESIGN

This study is a Phase 3, multicenter, 56-week, randomized, open-label for the drug (efpeglenatide, dulaglutide) and double-blind for the doses of efpeglenatide, active-controlled, 3-arm, parallel group study.

Eligible participants will be randomized 1:1:1 ratio to receive 1 of 2 dose levels of efpeglenatide (4 or 6 mg) or dulaglutide (1.5 mg), to be administered SC once weekly. Randomization will be stratified by HbA1c (<8%, ≥8%) at screening and BMI (<30 kg/m^2 and ≥30 kg/m^2) at Visit 3 (Day -1). Masked dose escalation over the course of 4 weeks will be used to reach the assigned 4 and 6 mg efpeglenatide weekly doses. For efpeglenatide arms, the escalation will start from 2 mg once weekly to the maximum of 4 or 6 mg once weekly, as assigned at randomization. Participants randomized to the dulaglutide 1.5 mg dose arm will initiate dosing at 0.75 mg once weekly and will increase after 2 weeks to 1.5 mg once weekly for the treatment duration.

The study will be comprised of 3 periods as follows:

- An up to 3-week Screening Period (with a minimum 11 days)
- A 56-week open label, active controlled Treatment Period, for efficacy and safety assessments
- A 6-week post-treatment Follow-up Period to collect safety information after last dose of IMP (treatment completed or permanent treatment discontinuation)

The maximum study duration per participant will be 65 weeks.

### 4.2 SCIENTIFIC RATIONALE FOR STUDY DESIGN

This study is designed to demonstrate the efficacy and safety of efpeglenatide in comparison to dulaglutide, in participants with T2DM inadequately controlled with metformin.

Dulaglutide was chosen as the comparator as it is dosed once weekly (the same frequency as efpeglenatide), provides HbA1c lowering similar to liraglutide, weight reduction similar to exenatide, and has similar safety profile to exenatide and liraglutide (7).

The study is also designed to assess and compare the tolerability and participant's perspective on treatment benefit and risk.

Bias will be minimized by randomizing the participants to treatment groups, blinding the participants and the Investigators to efpeglenatide dose allocations, and by adjudicating the selected AEs in a blinded fashion.

A parallel-group, randomized, active-controlled design was selected because trial participants are exposed to a single treatment and dose, and assignment to that treatment is based solely on chance. This design is free of the limitations of competing designs such as crossover, in which there may be a carryover of effect from the first to the second treatment. While the sample size of the parallel-group design is larger to account for more variability when participants cannot serve as their own control, the above-mentioned limitations of the crossover design have led the randomized, controlled trial design to be the standard for therapeutic confirmatory trials for regulatory approval such as this trial.

### **4.3 JUSTIFICATION FOR DOSE**

The selection of efpeglenatide 4 mg and 6 mg once-weekly doses is based on the results of early phase studies.

Efpeglenatide has shown increasing efficacy up to the highest dose tested. The once-weekly 4 mg dose has shown clinically relevant efficacy (studies HM-EXC-202 and HM-EXC-203). The once-weekly 6 mg dose tested in non-diabetic subjects in the Phase 2 study (HM-EXC-205) has shown higher efficacy in the decrease of body weight than the once-weekly 4 mg dose in this population. Most likely, higher efficacy of the 6 mg dose compared to the 4 mg dose can also be expected for glycemic control in diabetic patients.

Nausea and vomiting events appeared to be dose related and the trend over time showed an increase in incidence after the first injection with a general decrease thereafter for all tested doses. The 2 mg dose demonstrated good GI tolerability has been selected as the starting dose of both, the 4 and 6 mg efpeglenatide treatment groups in this study. Based on the observed general decrease of GI event incidence after the first week of treatment with efpeglenatide, dose increases to achieve 4 and 6 mg (in the corresponding arm) will be in 2 mg step intervals every 2 weeks in order to minimize the GI adverse effects. The escalation step of 2 mg is small enough to contribute to improvement of GI tolerability at dose increase. With this dose escalation schedule, the dose of 4 mg once-weekly will be achieved 2 weeks and the maximal dose of 6 mg once-weekly will be achieved only 4 weeks after the first dose of efpeglenatide.

Dulaglutide will be administered at 1.5 mg once weekly, as per approved label following an initiation to be started at 0.75 mg once weekly (5).

Please refer to the IB for more details (2).

### **4.4 END OF STUDY DEFINITION**

The end of the study is defined as the date of the last visit of the last participant in the study (as scheduled per protocol or if trial is stopped prematurely based on the advice of the independent DMC or other unforeseen development).

## 5 STUDY POPULATION

Prospective approval of protocol deviations to recruitment and enrollment criteria, also known as protocol waivers or exemptions, is not permitted.

### 5.1 INCLUSION CRITERIA

Participants are eligible to be included in the study only if all of the following criteria apply:

#### Age

I 01. Participant must be  $\geq 18$  years of age at the time of signing the informed consent

#### Type of participant and disease characteristics

I 02. Participants with T2DM

I 03. Diabetes diagnosed at least 1 year before screening

I 04. Participants on stable dose of at least 1500 mg/day of metformin, or maximum tolerated dose, or as per country regulation if less, for at least 3 months prior to screening

I 05. HbA1c between 7.0% and 10.0% (inclusive) measured by the central laboratory at screening

#### Informed Consent

I 06. Capable of giving signed informed consent which includes compliance with the requirements and restrictions listed in the informed consent form (ICF) and in this protocol

### 5.2 EXCLUSION CRITERIA

Participants are excluded from the study if any of the following criteria apply:

#### Medical conditions

E 01. Retinopathy or maculopathy with one of the following treatments, either recent (within 3 months prior to screening) or planned: intravitreal injections or laser or vitrectomy surgery

E 02. Clinically relevant history of GI disease associated with prolonged nausea and vomiting, including (but not limited to) gastroparesis, unstable and not controlled gastroesophageal reflux disease requiring medical treatment within 6 months prior to screening or history of surgery affecting gastric emptying

- E 03. History of pancreatitis (unless pancreatitis was related to gallstones and cholecystectomy has been performed), pancreatitis during previous treatment with incretin therapies, chronic pancreatitis, pancreatectomy
- E 04. Personal or family history of MTC or genetic conditions that predisposes to MTC (eg, multiple endocrine neoplasia syndromes)
- E 05. Body weight change of  $\geq 5$  kg within the last 3 months prior to screening
- E 06. Systolic BP  $>180$  mmHg and/or diastolic BP  $>100$  mmHg at randomization
- E 07. Severe renal disease as defined by estimated glomerular filtration rate (eGFR, by Modification of Diet in Renal Disease [MDRD]) of  $<30$  mL/min/1.73 m^2
- E 08. Laboratory findings at the Screening Visit:
  - Alanine aminotransferase (ALT) or aspartate aminotransferase (AST)  $>3 \times$  ULN or total bilirubin  $>1.5 \times$  ULN (except in case of documented Gilbert's syndrome)
  - Amylase and/or lipase:  $>3 \times$  ULN
  - Calcitonin  $\geq 5.9$  pmol/L (20 pg/mL)
- E 09. Known presence of factors that interfere with the HbA1c measurement (eg, specific hemoglobin variants, hemolytic anemia) compromising the reliability of HbA1c assessment or medical conditions that affect interpretation of HbA1c results (eg, blood transfusion or severe blood loss in the last 3 months prior to randomization, any condition that shortens erythrocyte survival)
- E 10. Any clinically significant abnormality identified either in medical history or during screening evaluation (eg, physical examination, laboratory tests, 12-lead ECG, vital signs) or any AE during screening period, which, in the judgment of the Investigator, would preclude safe participation in the study or constrains efficacy assessment

**Prior/concomitant therapy**

- E 11. Participants having received any antidiabetic drug other than metformin within 3 months prior to screening
- E 12. Participants having received any type of insulin for more than 30 consecutive days at any time (except for treatment of gestational diabetes)
- E 13. Systemic glucocorticoid therapy (excluding topical, intra-articular, or ophthalmic application, nasal spray or inhaled forms) for more than 10 consecutive days in the last 3 months prior to screening
- E 14. Participant not at a stable anti-obesity treatment (if taken) at least 3 months prior to the screening and not willing to maintain the dose stable during the study

- E 15. Gastric surgery or other gastric procedures intended for weight loss within 2 years prior to screening, or planned during study period

**Prior/concurrent clinical study experience**

- E 16. Participation in any previous clinical trial of efpeglenatide/SAR439977
- E 17. Exposure to any investigational drugs in the last 4 weeks or 5 half-lives, whichever is longer, prior to screening
- E 18. Concomitant enrollment in any other clinical study involving an investigational study treatment or any other type of medical research

**Other exclusions**

- E 19. Hypersensitivity to any of the study treatments, or components thereof, or to any GLP-1 RAs
- E 20. History of drug or alcohol abuse within 6 months prior to screening
- E 21. Pregnant (confirmed by serum pregnancy test at screening) or breast-feeding women
- E 22. Women of childbearing potential (WOCBP) not willing to use highly effective method(s) of birth control (Appendix 4 [[Section 10.4](#)]) or who are unwilling to be tested for pregnancy during the study period and for at least 5 weeks after the last dose of study intervention
- E 23. Participant is an employee of the Sponsor, or is the Investigator or any subinvestigator, research assistant, pharmacist, study coordinator, other staff or relative thereof directly involved in the conduct of the protocol
- E 24. Any country-related specific regulation that would prevent the subject from entering the study
- E 25. Individuals committed to an institution by virtue of an order issued either by the judicial or the administrative authorities

**Additional criteria at the end of the Screening Period**

- E 26. Participants unwilling or unable to comply with study procedures as outlined in the protocol
- E 27. Participants who withdraw consent during the screening period (starting from signed ICF)

## 5.3 LIFESTYLE CONSIDERATIONS

### 5.3.1 Meals and dietary restrictions

#### Diet and exercise

Lifestyle and diet therapy provided before the time of screening is to be continued during the study. Individualized dietary and lifestyle counseling will be given by a healthcare professional as per Schedule of Activities (SoA; [Section 1.3](#)) and should be consistent with international or local guidelines for participants with T2DM (for example, see [8]).

#### Fasting conditions

- For Visits 3 (Day 1), 6 (Week 8), 7 (Week 12), 10 (Week 30), 12 (Week 43), and 14 (Week 56), participants need to come to the study center in a fasting condition after an overnight fast of no less than 8 hours which consists of no food or liquid intake, other than water. The participants should not take any antidiabetic medication before blood sampling.
- Fasting (before breakfast and before administration of antidiabetic medication) self-monitored plasma glucose (SMPG) must be performed per SoA ([Section 1.3](#)).

## 5.4 SCREEN FAILURES

Screen failures are defined as participants who consent to participate in the clinical study but are not subsequently randomized (randomly assigned to study intervention). A minimal set of screen failure information is required to ensure transparent reporting of screen failure participants to meet the Consolidated Standards of Reporting Trials (CONSORT) publishing requirements and to respond to queries from regulatory authorities. Minimal information includes demography, screen failure details, eligibility criteria, and any serious adverse event (SAE).

Individuals who do not meet the criteria for participation in this study (screen failure) may be rescreened once in cases where the original screen failure was due to reasons expected to change at rescreening (based upon the Investigator's clinical judgment). A participant should not be randomized more than once (ie, entering the randomized period twice).

## 6 STUDY INTERVENTION

Study intervention is defined as any investigational intervention(s), marketed product(s), placebo, or medical device(s) intended to be administered to a study participant according to the study protocol.

The IMP includes efpeglenatide in 3 doses (2, 4, and 6 mg; the 2 mg dose will be used for titration only) and dulaglutide in 2 doses (0.75 mg and 1.5 mg solution; the 0.75 mg dose will be used for titration only).

Non-IMP (NIMP) includes metformin administered as per Investigator prescription and in accordance with local labeling, and rescue medication(s) that will be used to treat hyperglycemia if a participant's glycemic values reach the applicable rescue threshold as defined in [Section 6.1.2.2](#).

### 6.1 STUDY INTERVENTION(S) ADMINISTERED

**Table 2 - Overview of study interventions administered**

Study intervention name	Efpeglenatide	Dulaglutide (Trulicity™)
Dosage formulation	Sterile, non-pyrogenic, clear, colorless solution in a disposable single-dose autoinjector in the formulation buffer (containing citric acid monohydrate, L-methionine, polysorbate 20, D-mannitol, sodium hydroxide and water for injection)	Sterile, non-pyrogenic, clear, colorless solution in a single-dose pen in the formulation buffer (containing citric acid anhydrous, mannitol, polysorbate 80, trisodium citrate dehydrate in water for injection)
Unit dose strength(s)/Dosage level(s)	2 mg/500 µL, 4 mg/500 µL, and 6 mg/500 µL	0.75 mg/0.5 mL and 1.5 mg/0.5 mL
Route of administration	SC injection	SC injection

**Dosing instructions**

The injection interval of the IMP is once weekly, preferably on the same week day (eg, each Monday) at any time of the day. Injections should be administered SC to any of the following body regions: abdomen, thigh, or upper arm. Within any selected region, the site of injection should be changed (rotated) at each time to prevent skin reactions. The region, date, and time of administration should be recorded for each injection administered.

For selected visits during the Treatment Period up to Week 30 (corresponding to predose PK sample collection) the weekly dose will be administered at the study site after blood sample collection (see SoA, [Section 1.3](#)).

For the other weekly administrations, if a dose is missed, participants must be instructed to administer it as soon as possible if there are at least 3 days (72 hours) until the next scheduled dose. If less than 3 days remain before the next scheduled dose, the participant should skip the missed dose and administer the next dose on the regularly scheduled day. In each case, participants can then resume their regular once-weekly dosing schedule. The day of weekly administration can be changed if necessary as long as the last dose was administered 3 or more days before (see [Section 7.1.2.1](#)).

Participants will be asked to administer the last 2 consecutive weekly dose injections prior to PK sampling at the same body region (eg, at Week 2 and Week 3 before the planned PK visit at Week 4; see [Section 8.5](#)).

Predose PK samples are expected to be collected at least 6 to 7 days after last dose of IMP. The corresponding study visits (Visit 5, Visit 7, Visit 9 and Visit 10) and the timing of dose administration before each of these visits should be scheduled to ensure, as much as possible, the duration of 6 to 7 days between them is maintained.

**IMP dose schedule**

	Dose 1	Dose 2	Dose 3	Dose 4	Dose 5
	Day 1	Week 1	Week 2	Week 3	Week 4
	Visit 3		Visit 4		Visit 5
Dosing	(on-site)	(at home)	(on-site)	(at home)	(on-site)
Epeglenatide 4 mg	2 mg	2 mg	4 mg	4 mg	4 mg
Epeglenatide 6 mg	2 mg	2 mg	4 mg	4 mg	6 mg
Dulaglutide 1.5 mg	0.75 mg	0.75 mg	1.5 mg	1.5 mg	1.5 mg

From Week 4 (Visit 5) through the rest of the treatment period, participants will remain on the randomized IMP dose until the EOT at Week 56 (Visit 14).

**Storage conditions** Store between +2°C and +8°C (36°F and 46°F). Do not freeze, protect from light.

**Packaging and labeling** Study treatment will be provided in boxes, in accordance with the administration schedule. The content of the labeling is in accordance with the local regulatory specifications and requirements.

The details of this table are specific to IMP; information of non-IMP is described separately in this [Section 6.1.2](#).

EOT: end of treatment, IMP: investigational medicinal product, PK: pharmacokinetics, SC: subcutaneous, SoA: schedule of activities

### 6.1.1 Investigational medicinal products

The appropriate number of kits will be dispensed for the period until the next dispensing visit (please refer to SoA, [Section 1.3](#)). Storage conditions and use-by-end date (when required by country regulations) are part of the label text.

Participants will be trained on the use of the autoinjector by the study staff at Visit 2 (Day -7 [ $\pm 3$  days]) and provided with an “instructions for use” leaflet, which will describe the handling procedures for the autoinjector and administration technique. Injection training pads can be used, if needed. Initial injection technique training at Visit 2 (Day -7 [ $\pm 3$  days]) will include self-injection with a training autoinjector and assessment of participant’s skills and understanding by observing teach-back (if needed). Also, if needed, an additional training autoinjector can be used for self-injection technique training any time prior to the day of randomization.

Review of injection technique can be done at any other visit as needed (self-injection with IMP at site during selected visits until Week 30, under close supervision).

Review of injection sites will be performed at all on-site visits.

Autoinjector-related issues (malfunctions) should be reported to the Sponsor by the means of a procedure on Product Technical Complaint (PTC) forms, which are described in the Pharmacy Manual.

In case of emergency only, for scheduled or unscheduled visits, the IMP might be supplied from the site to the participant via a Sponsor-approved courier company where allowed by local regulations. Direct-To-Patient (DTP) remains an option and the participant/investigator can refuse this option.

## **6.1.2 Noninvestigational medicinal products**

### **6.1.2.1 Background medication**

#### *Metformin*

- Route of administration: Oral
- Dose regimen: Administered as per the Investigator’s prescription and in accordance with local labeling. Participants are enrolled with metformin at a stable dose ( $\geq 1500$  mg/day, maximum tolerated dose, or as per country regulation if less) for at least 3 months prior to the Screening Visit. The dose should be kept stable throughout the study unless dose reduction is needed for safety reasons.

### **6.1.2.2 Rescue therapy**

Rescue medication(s) that will be used to treat unacceptable hyperglycemia, if a participant’s glycemia reaches an applicable rescue threshold is considered NIMP for this study. The threshold values are defined in [Table 3](#) and are dependent on study period.

**Table 3 - Rescue criteria**

Time in Study	Threshold
From randomization up through the scheduled Week 8 visit (Visit 6)	FPG >15.0 mmol/L (>270 mg/dL)
After the Week 8 visit (Visit 6) up through the scheduled Week 12 visit (Visit 7)	FPG >13.3 mmol/L (>240 mg/dL)
After the Week 12 visit (Visit 7) through the end of Week 30 visit (Visit 10)	FPG >11.1 mmol/L (>200 mg/dL) or HbA1c ≥8.5%
After the Week 30 visit (Visit 10) through the end of the treatment period (Week 56 [Visit 14])	FPG >10.1 mmol/L (>180 mg/dL) or HbA1c ≥8.0%

FPG: fasting plasma glucose, HbA1c: hemoglobin A1c

Routine fasting SMPG and central laboratory alerts on FPG (and HbA1c at Week 12 [Visit 7] onwards) will be set up to ensure that glycemic parameter results remain below the predefined thresholds.

- If a fasting SMPG value exceeds the specific glycemic limit on 1 day, the participant must check it again during the following 2 days. If all the SMPG values in 3 consecutive days exceed the specific limit, the participant should contact the Investigator and a central laboratory FPG measurement (and HbA1c from Week 12 [Visit 7] onwards) should be performed as soon as possible for confirmation.
- Upon receipt of a central laboratory alert for either FPG or HbA1c, a central laboratory re-test must be completed and confirmed as exceeding the threshold for rescue before rescue therapy is initiated. The re-test confirmation should be performed as soon as possible during an unscheduled visit.

In the event that a confirmatory FPG and/or HbA1c value exceeds the threshold, the Investigator should ensure that no reasonable explanation exists for insufficient glucose control and in particular that:

- The increased FPG has been tested at a fasting status (ie, no food or liquid intake [except water] for ≥8 hours)
- IMP was appropriately injected (as per weekly schedule)
- There was no intercurrent disease, which may jeopardize glycemic control (eg, infectious disease)
- Compliance to treatment was appropriate
- Compliance to diet and lifestyle was appropriate

If any of the above-mentioned explanations can reasonably explain the insufficient glycemic control, the Investigator should consider not initiating rescue medication(s) and should undertake appropriate action as follows:

- Assess FPG (ie, after the participant has fasted for ≥8 hours)
- Initiate an evaluation and treatment of intercurrent disease (to be reported in AE/concomitant medication parts of the electronic Case Report Form [eCRF] and the medical record)

- Stress the absolute need for the participants to be compliant with treatment
- Organize a specific interview with the participants and a Registered Dietician or other qualified nutrition professional to reinforce the absolute need to be compliant with diet and lifestyle recommendations, and schedule an FPG and/or HbA1c assessment at the next visit

If none of the above-mentioned reasons can be found, or if an appropriate action fails to decrease FPG and/or HbA1c to below the threshold values, rescue medication(s) may be introduced.

If a participant needs to start rescue therapy, an unscheduled in-person visit will be scheduled to perform pre-rescue assessments (which are the same as those specified for EOT; Week 56 [Visit 14]), prior to starting the rescue medication(s).

Prescription of open-label rescue medication(s) to treat hyperglycemia will be at the discretion of the Investigator and in accordance with local standards of care and prescribing practice. With the exception of other GLP-1 RAs and DPP-4 inhibitors, any approved medication(s) can be prescribed to treat the hyperglycemia.

If a participant requires glycemic rescue, the IMP received during the randomized, open-label Treatment Period should be continued (unless the Investigator considers a change necessary for safety reasons) and the efpeglenatide dose must remain blinded until the end of the study.

All concomitant antidiabetic medications (background metformin and/or rescue therapy) will be documented in the eCRF. The cost of NIMPs not covered by health insurance will be reimbursed by the study Sponsor where permitted by local regulations.

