- In 3 large Phase 2 clinical studies with efpeglenatide (HM-EXC-203, HM-EXC-204, and HM-EXC-205), overall, a total of 12 out of 571 participants on efpeglenatide and 3 out of 183 participants on comparators had post baseline alanine aminotransferase (ALT)

elevation  $\geq 3 \times$  upper limit of normal (ULN) and most had confounding factors (2). In this study, patients with elevated liver enzymes  $>3 \times$  ULN or total bilirubin  $>1.5 \times$  ULN (except in cases of Gilbert's syndrome) will be excluded from participation. Liver function tests will be done regularly throughout the study.

Efpeglenatide concentrations will also be sampled in study EFC14829. These sparse pharmacokinetic (PK) samples will be used for population PK analyses to determine the PK characteristics of efpeglenatide in the target T2DM population.

The risks to the study participants will be minimized by careful participant selection according to appropriate inclusion and exclusion criteria based on existing nonclinical and clinical data. During the study, participants will be closely monitored at the regular visits, including physical examinations and laboratory tests to monitor the glucose-lowering effects and to early detect eventual adverse reactions. Suggested actions and follow-up measurements for laboratory abnormalities and other safety findings are provided in Appendix 5 (Section 10.5) of the protocol.

All participants will receive active treatment which is expected to contribute to lower the plasma glucose. Participation in the study may also increase motivation and result in an improvement of glycemic control. The HbA1c and FPG tests will be performed approximately every 3 to 4 months. Participants will be provided with a glucose meter and test strips to regularly self-measure their plasma glucose. Central laboratory alerts on FPG and on HbA1c (from Week 12 onwards) will be set up to ensure that glycemic parameters remain under predefined rescue thresholds. Close monitoring throughout the study will detect deterioration of glycemic control and allow initiation of "rescue therapy" as deemed necessary.

More detailed information about the known and expected benefits and risks and reasonably expected AEs of efpeglenatide may be found in Section 2 Summary and Section 7 Summary of Data and Guidance for the Investigator, respectively, of the IB (2), and the according information related to dulaglutide may be found in the prescribing information for TRULICITY (5).

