### 6.3.1 Methods of blinding

The entire treatment period will be open-label for the drug (efpeglenatide, dulaglutide) and double-blind (for Investigators and participants) for the active doses (4 mg, 6 mg) of efpeglenatide. Efpeglenatide will be provided as a single-dose autoinjector and dulaglutide as a single-dose pen for self-injection. Each titration and treatment kit will be labeled with a unique number. The list of kit numbers will be generated by Sanofi.

In accordance with the study design, Investigators will remain blinded for the doses of efpeglenatide and will not have access to the randomization (dose) codes except under exceptional medical circumstances.

Members of the CEC will review and adjudicate events in a blinded manner (please also refer to Appendix 1 [[Section 10.1](#)]).

The Investigator will not have access to the data of the primary efficacy endpoint (ie, HbA1c) or FPG obtained after Baseline/Randomization visit (Day 1; Visit 3) as those data will be masked. If the central laboratory detects FPG above the rescue thresholds, the Investigator will receive an alert from the central laboratory (see [Section 6.1.2.2](#)). The HbA1c alerts will also be sent if a value is above threshold at the Week 12 visit (Visit 7) and onwards.

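### Table 3 gives no HbA1c rescue threshold for the Week 12 visit, although four places in the protocol order HbA1c alerts from that visit

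*Protocol*

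**What the plan says.** Section 6.1.2.2 states that the rescue thresholds are the ones in Table 3 and that they depend on the study period. Two rows meet at Week 12:

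- The second row covers "After the Week 8 visit (Visit 6) up through the scheduled Week 12 visit (Visit 7". Its only entry is "FPG >13.3 mmol/L (>240 mg/dL".
- The third row covers "After the Week 12 visit (Visit 7) through the end of Week 30 visit (Visit 10". Its entry is "FPG >11.1 mmol/L (>200 mg/dL) or HbA1c ≥8.5" (percent). This is the first HbA1c limit in the table.

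The alert text starts HbA1c alerting one step earlier:

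- Section 6.1.2.2, under Table 3: "central laboratory alerts on FPG (and HbA1c at Week 12 [Visit 7] onwards) will be set up".
- Section 6.3.1: "The HbA1c alerts will also be sent if a value is above threshold at the Week 12 visit (Visit 7) and onwards".
- Section 2.3: "Central laboratory alerts on FPG and on HbA1c (from Week 12 onwards) will be set up".
- Section 1.3, rescue therapy note in the Schedule of Activities: the same starting point, Week 12 (Visit 7). SAP Appendix D repeats the note.

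Section 6.3.1 also masks post-baseline HbA1c and FPG to the investigator. After an alert, a central re-test at an unscheduled visit has to be "confirmed as exceeding the threshold for rescue before rescue therapy is initiated". The investigator then looks for another explanation, such as non-fasting status, poor compliance or intercurrent illness. If there is none, or if corrective action fails, rescue is permitted.

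**The concern.** An alert needs a number to compare with. For the HbA1c drawn at Visit 7, Section 6.3.1 speaks of a threshold at that visit, but Table 3 has none. The central laboratory has to program something, and the protocol does not say what.

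Two things are at stake. The first is a participant safeguard. Section 2.3 presents these alerts as the means of keeping glycemic values within the rescue limits, and masking means that a site does not otherwise see a scheduled HbA1c result. The second is the timing of rescue between Weeks 12 and 30. This feeds directly into the exploratory rescue endpoints, and indirectly into the Week 56 HbA1c analysis, which keeps values obtained after rescue.

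**Working it through.** There is no plan figure to reproduce for this point, so the check sets the passages side by side and adds simple visit arithmetic.

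**1. Which row holds the Week 12 sample?** The second row runs up to and including the scheduled Week 12 visit; the third starts after it. A sample drawn at Visit 7 therefore belongs to the second row.

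| Source | HbA1c limit for the Visit 7 sample | HbA1c alert on the Visit 7 sample |
|---|---|---|
| Table 3, second row | none | not possible without a limit |
| Table 3, third row | ≥8.5%, but starts after Visit 7 | does not cover Visit 7 |
| Text under Table 3 | none given | yes |
| Section 6.3.1 | refers to a threshold, gives no value | yes |
| Section 2.3 | refers to rescue thresholds, gives no value | yes |
| Section 1.3 note | none given | yes |

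The table and the alert text cannot both be followed for this one sample. FPG has no such gap, because the second row gives an FPG limit for the visit.

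**2. Which step is affected?** Only the first alert. Any re-test comes after Visit 7 and so falls in the third row, where the HbA1c limit is stated.

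**3. When is the next scheduled HbA1c?** SAP Appendix D, in agreement with the visit list in the SAP Appendix A code, schedules on-treatment HbA1c at Weeks 12, 30, 43 and 56.

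- Nominal gap: Day 210 − Day 84 = 126 days; 126/7 = 18.0 weeks.
- Shortest, with ±3-day windows: (210 − 3) − (84 + 3) = 120 days = 17.1 weeks.
- Longest: (210 + 3) − (84 − 3) = 132 days = 18.9 weeks.

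**4. What still operates in that gap?** The FPG drawn at Week 12 has a limit and an alert. The next scheduled central FPG is also at Week 30 (SAP Appendix D: Weeks 8, 12, 30, 43, 56). In between, fasting self-monitored plasma glucose (SMPG) is scheduled around the Week 18, 24 and 30 visits. If it exceeds the limit on three consecutive days, Section 6.1.2.2 calls for a central FPG and, from Week 12, a central HbA1c. The FPG limit in force also falls from 13.3 to 11.1 mmol/L after Week 12.

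**5. Which analyses could it reach?** Rescue use until Weeks 30 and 56 and time to rescue are exploratory (Protocol Table 1). The SAP summarises them descriptively, with a Kaplan-Meier curve for time to rescue. The primary analysis includes post-rescue HbA1c in all arms, so the link runs from alert to re-test to a possible rescue to the Week 56 value. The sample size does not depend on the rescue rule. Its stated 91% power reproduces: SE = 1.1 × √(2/300) = 0.0898; 0.3/0.0898 − 1.96 = 1.38; Φ(1.38) = 0.916.

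**The case against.** The strongest reply is that this is a slip at a row edge. Four places include Week 12 in HbA1c alerting and only the boundary of one table row says otherwise. Reading Table 3 literally would leave the explicit mention of Visit 7 in Section 6.3.1 without effect. The re-test that gates rescue has a stated limit. One central laboratory presumably ran one setting, and its specification is not among the documents, so inconsistent alerting between sites is not shown.

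Most of this stands. It shows that alerting at Week 12 was probably meant, but it does not supply the value, and an alert cannot be programmed without one.

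A reader might infer more than the documents support:

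- *That a Week 12 result either starts rescue or is ignored for 18 weeks.* It can only start an alert, a re-test and a check for other explanations. The 18 weeks is the interval between scheduled HbA1c samples, and the SMPG route can produce an unscheduled HbA1c within it. For the same reason, Week 30 is not the first HbA1c that could lead to rescue.
- *That the at-or-above limits in Table 3 conflict with the alert and confirmation text, which speaks of values above or exceeding the threshold.* Table 3 is the named source of the limits. Elsewhere Section 6.1.2.2 speaks of glycemia reaching a threshold and of results staying below it, which fits the table. The looser wording is worth aligning, but it is not a second rule.
- *That the gap favours an arm.* By Week 12 the 6 mg arm has had 8 weeks at its assigned dose, and the 4 mg and dulaglutide arms 10. That follows from titration and would hold under any wording of Table 3; the rescue rule is the same in all arms.
- *That a given number of participants is affected.* The documents give no expected Week 12 HbA1c distribution. A count of high Week 12 values would in any case not be a count of changed rescue decisions.

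**Conclusion.** The inconsistency is real and is in the current text: the scheduled Week 12 HbA1c has to be alerted against a threshold that Table 3 does not state for that visit. It concerns one sample per participant and one step, the initial alert. If the laboratory followed Table 3 to the letter, a high Week 12 HbA1c would go unreported to the site, and the next scheduled HbA1c would come 18.0 weeks later (17.1 to 18.9 with visit windows), with FPG and SMPG monitoring as the remaining safeguards.

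The effect on the primary comparison is indirect and cannot be quantified from the documents. Nothing here shows that the noninferiority conclusion would change. The conclusion rests on the literal row wording and on the sampling weeks in the SAP. The laboratory alert specification could show that the matter was settled in practice. This is a wording correction worth making because a decision threshold and a safeguard depend on it.

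**What to change.** Reconcile the Week 12 row boundary in Table 3 with Sections 1.3, 2.3, 6.1.2.2 and 6.3.1. State in Table 3 which row governs the sample drawn at the Week 12 visit, and check the central laboratory alert specification against that statement. In the same edit, make the alert and confirmation wording use the HbA1c inequality in Table 3. The sponsor's clinical team decides which rule and value apply.

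The cost is wording in one table and its cross-references, plus one check of the alert specification. No visits, samples or analyses are added. Because SAP Section 2.3.1.2 records that the sponsor ended the study early, a note beside the rescue summaries saying which setting the laboratory ran for Visit 7 would serve a reader of the results.
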